Everyday cognitive function	Everyday Cognition Scale (range: 1 to 4)	Informant-rated questionnaire	4 months, 6 months, and 12 months
Depressive symptoms	Geriatric Depression Scale (range: 0 to 15)	Survey completed by participants	4 months, 6 months, and 12 months
Sleep quality	Pittsburgh Sleep Quality Index (range: 0 to 21)	Survey completed by participants	4 months, 6 months, and 12 months
Quality of life	EuroQol EQ-5D (range: -1 to 1)	Survey completed by participants	4 months, 6 months, and 12 months

Randomization

Method of randomization

Eligible participants will be randomized to one of the three intervention groups with an allocation of 1:1:1 through a permuted block randomization method with a block size of 3 or 6 to prevent anticipation of assignment to the study group. The project data analyst, who will not be involved in the recruitment of participants, will use computer software (nQuery, version 4.0, Statistical Solutions Ltd) to generate a randomization schedule, which will be kept in a sealed envelope. No one else on the project will be

involved in generating the randomization. The schedule will be released by the data team to a research assistant before each wave of recruitment is scheduled. On the day of the assignment, the research assistant will assign qualified individuals to the intervention groups. The allocation sequence assigns individuals in the order that they were scheduled for baseline assessment. Randomization will occur after informed consent is obtained and baseline assessments have been completed.

Allocation concealment

To control for selection bias, all study assessors who collect study outcome measures will be blinded to the main study design and group allocation. Blinding will be strictly maintained by emphasizing to assessors the importance of minimizing assessment bias and by random checking of the blinding status. Efforts will be also made to maintain separation between the study assessors and research assistants who deal with administrative activities and class safety monitoring, and between study assessors and class instructors who deliver the intervention classes. Because of the nature of the interventions, study participants and interventionists will not be masked to group allocation. Participants will be instructed not to reveal their group status to the assessment staff at any time during follow-up.

Statistical interim analyses and stopping guidance

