None. However, annual data and safety information related to the project will be presented to the project Safety Officer appointed by the funding agency. The Safety Officer will determine whether any interim statistical analyses will be necessary and whether data collection continues on the basis of the project progression on subject recruitment, study assessment, or intervention adherence.

The following describes our pre-specified data analysis plan. Data will be coded to maintain group allocation blinding during analysis.

Descriptive analyses

- *Trial flow.* Information on the number of individuals screened, excluded, and qualified per the study eligibility criteria and assigned to the intervention, as well as the follow-up status, at each assessment time point will be presented in a figure in accordance with the CONSORT guidelines.
- *Comparability of intervention groups*
 - Baseline characteristics of the study population will be summarized by intervention group using summary statistics (e.g., mean, standard deviation, range, frequencies, or percentages) for continuous variables and frequency or percentages for categorical variables. Median IQRs will be calculated for variables that are not normally distributed.
 - Participants' characteristics ascertained at baseline will be compared across intervention groups using independent samples or Wilcoxon rank sum tests, as appropriate, for continuous variables and a chi-square or Fisher's exact tests, as appropriate, for categorical variables. Although no significant differences are expected due to the randomized intervention assignment and the relatively large sample size, any variables found to be significantly different will be noted and accounted for, by controlling for them as covariates in supplements to the main analyses.
- *Time-specific and change scores.* Scores at each follow-up and change in mean scores from baseline at 24 weeks, by intervention group, for all outcome measures will be calculated and presented.
- *Intervention adherence, attrition, and retention.* Class attendance data will be calculated as the average number of scheduled intervention sessions (48 total) attended by participants across intervention groups. Study attrition and retention rates will also be calculated and reported, by intervention group, as the number of participants who completed the 24-week intervention and those who completed all scheduled study follow-up assessments.

Analysis populations

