Efficacy analyses. The effect of intervention on the co-primary study outcomes will be evaluated using an intention-to-treat approach in which participants will be analyzed according to randomization assignment. A modified intention-to-treat analysis will be conducted that includes all participants who have undergone randomization and have completed all study follow-up assessments, regardless of their participation adherence status. Finally, a per-protocol analysis will include participants in the intention-to-treat population who have an overall class attendance rate of $\geq 75\%$ (out of the total planned 48 intervention class sessions) of their assigned exercise intervention.¹⁰

Co-primary endpoint analyses

To test the *Primary hypothesis*, we plan to use a generalized linear mixed model with random intercepts and fixed treatment effects for the primary outcomes. Specifically, we will determine the intervention effect through an analysis of a 3 (Group) by 3 (Time) mixed-effects model with repeated measures (follow-up time point) on the second factor (i.e., outcome measures assessed at baseline, 4 months [mid-point], and 6 months [intervention termination]).

In the presence of a Group by Time interaction effect, follow-up pair-wise comparisons, using independent t tests, will be performed to identify a priori specified between-group differences. Specifically, we will determine the intervention effect of cognitively enhanced tai ji quan for change in MoCA and costs of dual task in gait performance from baseline to 24 weeks by making a comparison between cognitively enhanced tai ji quan and standard tai ji quan and between cognitively enhanced tai ji quan and stretching exercise.

Level of statistical significance and confidence intervals. Our primary outcome analyses will be 2-sided with an adjusted significance level of <0.0125 ($0.05 / 4$ comparisons) and a 98.75% confidence interval (CI). For each group, both estimated means and their corresponding standard error of estimates at each assessment point will be presented. In presenting between-group differences, mean differences with CIs will be presented. SPSS “MIXED” function will be used in analyzing our primary outcomes.

Secondary and tertiary outcome analyses

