A similar analytic approach will also be applied to all secondary and tertiary (continuous) outcome variables described in Table 1. All study outcomes are expected to follow a normal distribution. In the case of deviation from normality, generalized estimating equations will be used to assess the effect of intervention over time. No Bonferroni correction will be made to account for multiple comparisons.

Level of statistical significance and confidence intervals. All tests and CIs will be 2-sided, and statistical significance will be defined as a P value of <0.05 . For each group, we will report both estimated means and their corresponding standard error of estimates at each assessment point. In presenting between-group differences at 24 weeks, estimated mean differences with CIs will be presented.

Analyses on examining intervention durability at 48-week follow-up

We will use the same analytic strategy outlined in our primary and secondary outcome analyses, with the exception of CDR-SB (described in detail below), to examine whether the intervention effects will persist 24 weeks after the end of the 24-week supervised interventions (*Secondary hypothesis*).

With the longitudinal data, we will test the hypothesis that the rate of improvement over time in the mean CDR-SB score, at 24-week post-intervention follow-up, will be greater in the cognitively enhanced tai ji quan group compared with the other two exercise groups. To test this hypothesis, we will use the latent growth curve modeling approach,³⁵ with maximum-likelihood estimation, analyzing the rate of change in the mean CDR-SB score defined by the four measurement time points: baseline, 16 weeks (mid intervention assessment), 24 weeks (end of intervention assessment), and 48 weeks (24 weeks post intervention follow-up).

[figure not shown]
Accordingly, we will operationalize our basic growth curve model with two latent growth factors: Intercept (defining the initial level of CDR-SB – baseline) and Slope (defining the rate of change over the course of the 48-week study period), with each factor being defined by the four time-specific CDR-SB

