measures. A schematic representation of the planned latent growth model to be evaluated for each intervention group is shown in Figure 1. The factor loadings for the Intercept factor will be fixed with a constant value of 1 for all measurement points whereas the loadings for the Slope factor, defining the rate of change over time, will be fixed at 0 for CDR-SB at baseline, 1 for CDR-SB at 16 weeks, 2 for CDR-SB at 24 weeks, and * for CDR-SB at 48 weeks (where * indicating an undefined, free estimate at 48 weeks). All other model parameters to be estimated include latent Intercept mean and its variance, latent Slope mean and its variance, the correlation between Intercept and Slope (covariance), and error variance for each of the four time-specific measurements (shown as E's). The model estimation will include all available data derived from the trial, hence, an intent-to-treat approach.

The model estimation of change in CDR-SB will involve two steps. First, we will estimate an unconditional latent growth model (i.e., without the group predictor [e.g., cognitively enhanced tai ji quan group vs standard tai ji quan group]). This unconditional growth curve model allows us to examine the overall pattern of change in the CDR-SB score over time. Next, a group predictor (as a binary variable [1=cognitively enhanced tai ji quan group and 2=standard tai ji quan group]) is added to the model parameterization. By regressing the Slope factor on to the predictor of the group variable, this model will examine the pre-specified intervention effect of the cognitively enhanced tai ji quan training, compared with each of other two active groups, individually, on the rate of change in cognitive functioning trajectories. The schematic representation of this second latent growth model with the group, as a predictor, is shown Figure 2 (next page). For reporting purposes, we will present (a) latent slope mean for each group and (b) the regression coefficient relating group and the latent slope (with 95% CI). A negative slope mean for CDR-SB will indicate an improvement in cognitive functioning and, therefore, a lowering of the disease progression, whereas a positive mean slope will indicate deterioration in cognitive functioning.

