All enrolled study participants will be followed until the trial period ends, whether or not the participant is still receiving or complying with the intervention. Primary endpoint analyses will be conducted according to the original randomization scheme in an intention-to-treat approach. We will use a multiple imputation data method for missing data. We plan to perform 10 sets of imputations. Variables without missing data to be used for prediction of imputed values on the study variables will include baseline measures of age, sex, level of education, MMSE, number of chronic conditions, and depression. The imputed data will be submitted to the same analytic model (i.e., linear mixed model) as the non-imputed observed data, and the results of each analytic model will be pooled across the 10 imputed data

sets. The secondary outcome analyses will also be conducted using the multiple imputation method described above. Tertiary outcome analysis will be conducted with observed data without imputation.

Interim analysis

We do not plan to perform any interim analyses for efficacy or futility. Instead, we will conduct interim monitoring performance with a focus on subject accrual, protocol adherence, intervention fidelity, data completeness and quality control, and intervention safety and analysis. Each is described below.

Subject accrual

We plan to conduct 10 staggered recruitment and enrollment waves, with approximately 35 participants planned at each wave, over 3.5 years of the 5-year project life. Each recruitment wave will be closely monitored at monthly staff meetings, with presentation of recruitment charts, to ensure we achieve our enrollment target. The accrual rate will be reviewed annually by research staff and will be reported to ORI IRB and the project Safety Officer appointed by NIA.

Protocol adherence

The overall intervention adherence (i.e., exercise class attendance) rate is defined as the sum of the total number of participants attending divided by the maximum number of 48 sessions planned, multiplied by 100, during the 6 months of active intervention. For the trial, the target adherence rate is $\geq 75\%$. Class attendance across the three study conditions will be closely monitored on a weekly basis by research staff and reviewed on a monthly basis by key personnel of the project. Participants who miss two consecutive sessions will be contacted by phone to ascertain the reason(s) for their absences and to encourage them to return.

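### The named imputation predictors omit randomised arm; applied as written, the 24-week between-arm difference shrinks by about the missing fraction (10% projected, 15% conservative)

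*SAP*

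**What the plan says.** The SAP section on noncompliance and missing data (repeated word for word in the SAP part of the protocol) plans 10 imputed data sets. It describes the fully observed variables that will predict "imputed values on the study variables will include baseline measures of age, sex, level of education, MMSE, number of chronic conditions, and depression". Randomised arm is not among the six, and neither is the participant's own outcome at any visit. The section does not name the algorithm, and it does not say whether imputation is run by arm or whether the 16-week outcome helps to predict the 24-week value.

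Other parts of the SAP bear on this:

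- Arm and baseline outcome are both available without gaps, since "Randomization will occur after informed consent is obtained and baseline assessments have been completed" (Method of randomization).
- The completed data enter a "3 (Group) by 3 (Time) mixed-effects model with repeated measures" (Co-primary endpoint analyses). On the link between imputation and analysis the plan says: "The imputed data will be submitted to the same analytic model (i.e., linear mixed model) as the non-imputed observed data".
- The approach extends beyond the co-primary outcomes: "The secondary outcome analyses will also be conducted using the multiple imputation method described above". Tertiary outcomes are not imputed.
- For durability at 48 weeks: "We will use the same analytic strategy outlined in our primary and secondary outcome analyses, with the exception of CDR-SB". The CDR-SB growth model is fitted by maximum likelihood, and "The model estimation will include all available data derived from the trial, hence, an intent-to-treat approach".

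**The concern.** An imputation model has to contain the terms that the analysis will estimate. If arm is left out, a missing 24-week value in the enhanced arm is drawn from a distribution averaged over all three arms, and so is a missing value in each comparator. The six listed covariates are measured before randomisation and are balanced in expectation, so they cannot bring the arm effect back. The imputed part of each arm then shows essentially no treatment difference, and the pooled contrast is pulled toward zero.

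At stake are the intention-to-treat contrasts for both co-primary outcomes and for the imputed secondary outcomes. The 48-week contrasts would be affected too if they are imputed the same way, and there Table 2 projects 15% missing. Leaving out the participant's own outcomes is a separate matter: with data missing completely at random it costs precision but does not bias the contrast.

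**Working it through.** **Inputs.** From the SAP power section: MoCA differences of 1.5 points (enhanced versus standard) and 3 points (enhanced versus stretching), SD 3.5, correlation 0.7, 267 evaluable participants (89 per arm), 15% loss, 315 in total (105 per arm), two-sided 0.05. From the co-primary section: two-sided 0.0125. From Table 2: 5% missing at 4 months, 10% at 6 months, 15% at 12 months.

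**The plan's own figure.** Power ≈ Φ(δ / (SD√(2/n)) − z). With δ = 1.5, SD = 3.5 and n = 89: 1.5 / 0.525 = 2.86, and 2.86 − 1.96 = 0.90, which gives 0.816. This agrees with the stated power above 80%. For the total, 267 / 0.85 = 314.1, rounded up to 315. Both figures reproduce.

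**Closed form with arm omitted.** Let a fraction f be missing completely at random and equally in each arm. Each arm's expected 24-week mean becomes (1 − f)μ_arm + f·μ_overall. The overall mean cancels in the contrast, leaving (1 − f) × the true difference.

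- 10% missing: 1.5 × 0.90 = 1.35; 3 × 0.90 = 2.70.
- 15% missing: 1.5 × 0.85 = 1.275; 3 × 0.85 = 2.55.
- Dual-task cost, 10% missing: 10% × 0.90 = 9.0%; 20% × 0.90 = 18%.
- Dual-task cost, 15% missing: 10% × 0.85 = 8.5%; 20% × 0.85 = 17%. The plan gives no SD for this outcome, so its power cannot be computed.

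**Unequal loss.** The simple rule no longer applies. Take changes of 3, 1.5 and 0 with 20%, 10% and 15% missing (enhanced, standard, stretching). The observed mean is (0.80×3 + 0.90×1.5 + 0.85×0) / 2.55 = 1.471. The enhanced arm becomes 2.4 + 0.20×1.471 = 2.694 and the standard arm 1.35 + 0.10×1.471 = 1.497. The difference is 1.197, a shrinkage of 20%. With 10%, 20% and 15% missing it is 1.347, about 10%.

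**Simulation to separate the causes.** 105 per arm; three visits with correlation 0.7; monotone missingness completely at random (5% at 16 weeks, 10% or 15% at 24 weeks); 10 proper normal-regression imputations pooled by Rubin's rules; random-intercept Group by Time model; 2,500 trials per setting. Assumed, because the documents do not give them: half of the effect present at 16 weeks, MMSE–MoCA correlation 0.5, the other five covariates unrelated to outcome. Results for a true 1.5-point difference, with 3.5 read as the SD of change and power at 0.0125:

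| Model | 10% missing: estimate / SE / power | 15% missing: estimate / SE / power |
|---|---|---|
| Listed predictors only | 1.344 / 0.552 / 0.467 | 1.271 / 0.580 / 0.348 |
| Listed + baseline outcome, no arm | 1.347 / 0.517 / 0.530 | 1.267 / 0.534 / 0.424 |
| Listed + baseline + 16 weeks, no arm | 1.366 / 0.510 / 0.570 | 1.299 / 0.520 / 0.491 |
| Listed + arm, no own outcomes | 1.499 / 0.549 / 0.578 | 1.498 / 0.579 / 0.529 |
| Listed + arm + own outcomes | 1.502 / 0.507 / 0.665 | 1.492 / 0.518 / 0.637 |
| Mixed model on observed data | 1.500 / 0.504 / 0.675 | 1.494 / 0.514 / 0.650 |

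If 3.5 is instead the raw-score SD (SD of change 3.5 × √(2 × 0.3) = 2.71), power in the same row order is 0.748, 0.815, 0.840, 0.866, 0.917, 0.922 at 10% missing, and 0.616, 0.722, 0.783, 0.813, 0.892, 0.895 at 15%.

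Adding arm removes the bias in every row. Adding own outcomes without arm does not. With 3.5 as SD of change and 10% missing, the power cost of omitting arm is 0.578 − 0.467 = 0.111 without own outcomes, or 0.665 − 0.570 = 0.095 with them. The rest of the gap between the first and fifth rows is lost precision.

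**Second simulation with other assumptions.** The six covariates explain 15% of outcome variance, and the 4-month effect is either nil or 67% of the 24-week effect. Listed predictors alone gave shrinkage of 9.0–9.9% and 14.9–15.5% at 10% and 15% missing. Adding baseline and 4-month outcomes without arm gave 9.6–10.0% and 15.0–15.3% with no 4-month effect, and 8.0–8.4% and 11.7–12.2% with the larger one. Including arm left between −0.9% and +0.4%.

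**No true effect** (1,500 trials, nominal 0.0125). Listed predictors only: rejection 0.004 and 0.002 at 10% and 15% missing. Arm plus own outcomes: 0.010 and 0.011.

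**The case against.** Five points can be made on the other side.

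- **Open wording.** The sentence says what the predictors include, not that they are the only ones, and it concerns complete variables. Follow-up outcomes have gaps and are themselves being imputed, so their absence from the list proves little. This stands for the outcomes. It does not explain the absence of arm, which has no missing values.
- **Unattenuated analyses exist.** The modified intention-to-treat analysis uses participants who completed all follow-ups, and the missing-data section may imply a mixed model on observed data. Both are unbiased if data are missing completely at random. At 89 completers per arm, power for 1.5 points at 0.0125 is 0.641 (SD of change 3.5) or 0.884 (raw SD 3.5, correlation 0.7), close to a corrected imputation. But the modified analysis is supporting, and the SAP does not say whether the imputed or the observed-data mixed-model result is primary. These analyses could reveal the shrinkage but would not correct the headline estimate.
- **Small and conservative.** At 10% missing the loss is 0.15 MoCA points, and both 1.35 and 1.275 stay above the 1.22-point stroke reference that the SAP cites. No false claim of benefit follows. This stands and limits the severity.
- **Not exactly the missing fraction.** Shrinkage is somewhat smaller if the 16-week outcome enters the imputation, and different if loss is unequal. This stands. Relief from the 16-week outcome may be slight for enhanced versus standard, because the protocol's Intervention section places the integrated cognitive phase in weeks 16 to 24.
- **Power loss has two causes.** This also stands, and the table separates them.

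**Conclusion.** The concern holds in conditional form. If the named list is used as written, the 24-week contrasts are understated by about the missing fraction, 10% as projected or 15% on the conservative allowance. Omission of arm is the sole cause of that bias. The result assumes data missing completely at random with equal loss across arms. The closed form and the simulations agree.

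The documents do not show that arm was in fact left out, so confidence that the reported analysis is affected is medium. The direction is conservative. The power figures depend on how 3.5 is read and on the stated assumptions; power below 80% even under the corrected imputation, with 3.5 as SD of change, is a separate issue (sized at 0.05, tested at 0.0125). The CDR-SB growth model is not affected. The plan should be corrected, because as written it does not protect its own primary estimate.

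**What to change.** State the full imputation model in the SAP and in the matching protocol text:

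- Impute separately by coded arm, or enter coded arm as a predictor. Analyst blinding is kept, because "Data will be coded to maintain group allocation blinding during analysis".
- Include the outcome at baseline, 16 and 24 weeks alongside the six listed covariates, and the 48-week value for durability analyses other than the CDR-SB growth model.
- Name the algorithm, and say whether the imputed or the observed-data result is primary.

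Alternatively, make the likelihood-based mixed model on all observed data primary and keep the corrected imputation as a sensitivity analysis.

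The SAP's title block cites a trial report dated 31 October 2023, so the sponsor should also state which imputation model produced the reported results and re-run it only if arm was left out. The cost is one SAP sentence and a few more variables in the imputation call, plus at most one re-analysis of stored data. No new data are needed.
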